Study Rationale	
This randomized, double-blind, placebo-controlled study of propranolol will shed important light on how sympathetic nervous system (SNS) activation influences psychological and inflammatory responses to acute stress. Results from this study will inform both the basic science literature that is attempting to map the physiological mechanisms by which psychological stress may lead to poor mental and physical health, and may also ultimately have therapeutic relevance for individuals who are experiencing high levels of stress that is putting their health at risk. Utilizing a psychopharmacological approach allows for the circumvention of many of the challenges of conducting this research in human populations, and will allow for conclusions regarding causality, given that SNS activation will be experimentally manipulated, rather than relying on correlational measures of SNS activity that are difficult to assess and are not appropriate for asking if SNS activity causes changes in psychology and biology.

Study Objective(s)	
Primary Objective 1. To determine if blocking beta-adrenergic receptors with the drug propranolol will attenuate inflammatory responses (i.e., interleukin-6; IL-6) to an acute, laboratory stressor.
 
Secondary Objective 1. To examine if blocking beta-adrenergic receptors with the drug propranolol will attenuate cortisol responses to an acute, laboratory stressor.
 
Secondary Objective 2. To examine if blocking beta-adrenergic receptors with the drug propranolol will attenuate salivary alpha amylase responses to an acute, laboratory stressor.
 
Secondary Objective 3. To evaluate if blocking beta-adrenergic receptors with the drug propranolol will attenuate sympathetic nervous system responses (i.e., pre-ejection period; PEP) to an acute, laboratory stressor.
 
Secondary Objective 4. To examine if blocking beta-adrenergic receptors with the drug propranolol will change parasympathetic nervous system responses (i.e., respiratory sinus arrhythmia; RSA) to an acute, laboratory stressor.
 
Secondary Objective 5. To examine if blocking beta-adrenergic receptors with the drug propranolol changes self-reported affective responses (i.e., negative affect) to an acute laboratory stressor.

Test Article(s)	Propranolol (FDA approved)

(If Applicable)

Study Design	This is a randomized, double blind, placebo-controlled study of the effects of propranolol on psychological and physiological responses to stress. It will consist of a telephone screening, an initial in-person session when consent will be obtained, and a subsequent longer, intervention session.
Subject Population	Inclusion Criteria 
1. Healthy individuals from the UNC-Chapel Hill community2. Ages 18-25.3. Fluent in English (spoken and written)4. In good overall health. Exclusion Criteria 
1) Presence or history of chronic physical illness (especially disorders with an inflammatory component, such as rheumatoid arthritis, asthma, allergies, or issues that can affect the heart, including low-blood pressure or other heart conditions)2) Presence or history of psychiatric illness (depression, anxiety)3) Any current prescription medication use4) Currently pregnant or planning to become pregnant (self-reported)5) Engagement in a number of health-compromising behaviors that may affect levels of pro-inflammatory cytokines, including cigarette smoking, excessive caffeine intake and sleep disturbance (e.g., working night shifts)6) Body Mass Index (BMI) greater than 30, given that adiposity is known to relate to baseline levels of inflammation;7) Anxiety about or previous history of problems with blood draws (e.g., fainting)8) Any reported heart conditions
Number Of Subjects	95 (45 per condition; we will run 5 “extra” subjects in the case of data loss)
Study Duration	Each subject’s participation will last 5-6 hours. The entire study is expected to last 1-2 years.
Study Phases	(1) Screening : screening for eligibility will occur via telephone interview, and consent will be obtained in-person during a first study session.
Screening	
Study Treatment	
Follow-Up	(2) Intervention : study intervention/experimental treatment will occur during a second study session. Participants will be randomly assigned to take either a single, 40 mg dose of propranolol, or a placebo, and will go through a standardized psychological stress task. Blood draws and saliva samples will be taken throughout, and will be assayed for inflammation and hormones, respectively. (3) Follow-Up : n/a
Efficacy Evaluations	This does not apply, as this is not a true interventional trial. These are healthy participants.

Safety Evaluations	The safety of the participants will be ensured by trained research staff and nurses from the UNC Clinical and Translational Research Center (CTRC), who will be on-hand for the intervention sessions, with the supervision of the PI. The co-investigating physician ([name]) will be on-call during all sessions, and the investigational drug service at UNC is available for consultation. A single dose of propranolol is expected to be very well-tolerated in this young, healthy population.
Statistical And Analytic Plan	To address our primary aim, we will conduct multilevel model (MLM) analyses examining levels of inflammation, with time (baseline, pre-stress, 30-, 60-, 90-min post-stress) as a within-subjects factor and condition (propranolol vs. placebo) as a between-subjects factor. We hypothesize that individuals in the placebo condition will show an increase in levels of the inflammatory marker IL-6 from pre- to post-stress, while those in the propranolol condition will show significantly lower levels of inflammation over time compared to the placebo condition (i.e., no stress-related increase in inflammatory markers). We will also conduct similar multilevel modelling analyses on our other secondary endpoints (i.e., cortisol, salivary alpha amylase, PEP, RSA, negative affect).
DATA AND SAFETY MONITORING PLAN	The PI and the project coordinator will be responsible for data quality management and ongoing assessment of safety. All data collected for the study will be stored on secure, password-protected servers maintained by the Department of Psychology and Neuroscience (or on secure, password-protected computers in the laboratory. Safety monitoring will be provided by the PI and the study physician, together with nurses from the UNC CTRC and the study coordinator.

1 BACKGROUND AND RATIONALE

1.1 Introduction

Psychological stress is implicated in the onset and progression of many common and costly chronic diseases, including cardiovascular disease, chronic pain conditions, and major depressive disorder (Cohen et al., 2007; Kendler et al., 1999; Steptoe and Kivimäki, 2012). An emerging body of evidence suggests that inflammation, indexed via levels of pro-inflammatory cytokines and reactive proteins, may be a key biological mechanism by which stress affects health (Baker et al., 2012; Miller et al., 2009; Slavich et al., 2010). Indeed, psychological stressors can induce increases in inflammation (Slavich and Irwin, 2014; Kiecolt-Glaser et al., 2003; Rohleder, 2014; Steptoe et al., 2007), and greater levels of inflammation may contribute to the development of disease (Capuron and Miller, 2004; Choy and Panayi, 2001; DellaGiola and Hannestad, 2010; Raison and Miller, 2013; The Emerging Risk Factors Collaboration, 2010). Despite this growing literature linking stress, inflammation, and poor health, little is known about the precise physiological mechanisms linking psychological stress and increases in inflammation.

One hypothesized mechanism that may translate psychological stress into increases in levels of inflammation is activation of the sympathetic nervous system (SNS). The SNS is part of the autonomic nervous system and is primarily indexed by release of the catecholamines epinephrine (adrenaline) and norepinephrine (noradrenaline). Prior research in non-human animal models has shown that stress-induced SNS activation leads to increases in levels of pro-inflammatory cytokines in inflammation (Bierhaus et al., 2003; DeRijk et al., 1994; Kop et al., 2008; van Gool et al., 1990), while pharmacologically blocking sympathetic activation attenuates the inflammatory response to stress (Bierhaus et al., 2003). However, no known human studies to date have examined the relationship between psychological stress, SNS activation, and inflammation. The present study is designed to address this major gap in our knowledge of the physiological mechanisms that may link stress and disease.

A potential reason for the lack of human research linking stress, SNS activation, and inflammation is that SNS activity is difficult to measure. Indeed, adrenaline and noradrenaline are released into the bloodstream very rapidly during a stressor, making their kinetics difficult to capture during typical laboratory-based stress paradigms. Indirect measures of SNS activity may be acquired using psychophysiological approaches that involve peripheral measures of electrical activity and efficiency of the heart; however, these methods provide only indirect indicators of SNS activity, making them subject to criticism in the psychoneuroimmunology community.

To circumvent these issues with assessment of SNS activity, the present study will employ a psychopharmacological approach to experimentally block SNS activity using the drug propranolol. Propranolol is a beta-blocker medication that is very commonly prescribed by physicians in the United States for the treatment of hypertension, given that it blocks adrenergic receptors that lead to relaxation of the cardiac muscle and smooth muscle tissue. Interestingly, propranolol is also sometimes prescribed to individuals who have performance anxiety (i.e., public speaking anxiety), as reducing SNS activity (i.e., eliminating the increased heart rate, blood pressure, sweaty palms, etc., that typically accompany anxiety-provoking situations) has been anecdotally observed to decrease perceptions of stress during these situations. Psychological scientists have recently become more interested in the role SNS activity may play in the formation and reconsolidation of fear memories, and a number of studies have now used propranolol to investigate if blocking SNS activity may help treat individuals with Post-Traumatic Stress Disorder (PTSD; Pitman et al., 2002; Vaiva et al., 2003). However, only one known study to date has investigated if propranolol reduces stress-induced immune system activation (Benschop et al., 1994), and this (now dated) study did not specifically explore if propranolol reduces inflammatory responses to stress. Furthermore, no known studies have examined if blocking SNS activity with propranolol changes individuals' appraisals of the stressful situation, or their affective responses to stress. Results from this study will complement and extend the existing work on how SNS activity affects fear memories and stress by focusing on how propranolol affects inflammatory and psychological responses to a stressor.

In addition to these primary goals of the present study, we will also explore the role of SNS activation in a number of additional tasks that are hypothesized to be affected by sympathetic arousal. More specifically, we will examine if exposure to propranolol eliminates implicit biases toward out-group members (in this case, African Americans), given that a very large literature suggests that many White Americans hold implicit biases against African Americans (Witenberk et al., 1997; Nosek et al., 2002). While it has been hypothesized that sympathetic arousal based on cultural stereotypes associating African Americans with negativity may be leading to these implicit biases, no known studies have investigated this issue. We will also explore of SNS activation is critical for empathy, or our ability to understand the emotional states of others, for avoiding risky decisions, and for moral judgments. Thus, this study will also answer a number of important, unanswered questions in social psychology regarding the role that sympathetic arousal plays in some of our most fundamental psychological processes.

In sum, this randomized, double-blind, placebo-controlled study of propranolol will shed important light on how SNS activation influences our psychological and inflammatory responses to stress. Results from this study will inform both the basic science literature that is attempting to map the physiological mechanisms by which psychological stress may lead to poor mental and physical health, and may also ultimately have therapeutic relevance for individuals who are experiencing high levels of stress that is putting their health at risk. By utilizing psychopharmacological approaches, we will circumvent many of the challenges of conducting this research in human populations, and we will also be in a place to draw strong conclusions regarding causality, given that we will have experimentally manipulated SNS activation, rather than relying on correlational measures of SNS activity that are difficult to assess and are not appropriate for asking if SNS activity *causes* changes in psychology and biology.

1.2 Name and Description of Investigational Product or Intervention

This study entails a one-time, 40 mg dose of short-acting propranolol to assess its immediate/short-term effects on inflammation, stress hormones, autonomic physiology, and psychological responses to an acute stressor. Propranolol is typically prescribed to treat hypertension and other heart-related conditions, but it sometimes used to treat performance anxiety. The participants enrolled in this study are medication-naïve, thus the administration of propranolol departs from the participant's routine clinical care.

1.3 Non-Clinical and Clinical Study Findings

Propranolol blocks the effects of epinephrine and norepinephrine by competitively binding to both β_1 - and β_2 -adrenergic receptors in both the peripheral and central nervous system. It was originally used to treat hypertension, approved by the FDA in 1965. Since then it has been FDA-approved for a variety of other indications, including migraine prevention, and essential tremor. It is even approved for certain pediatric conditions. Propranolol is one of the historically most commonly-used prescription medications, and it is generally viewed as a safe, nontoxic medication in the daily dosage range of up to 640 mg, divided into 2-4 doses per day. The 40mg dose to be given here is expected to be well-tolerated, with the most adverse side effect anticipated being the possibility of allergic reaction. Propranolol rarely causes side effects, including: hypotension, insomnia, fatigue, light-headedness, nausea, bronchospasm, dizziness, headache, hyperglycemia, and muscle weakness. Each of these side effects is uncommon at the low, single dosage being utilized in these studies. Moreover, these side effects are not only rare, but also quite mild and rarely prolonged (i.e. < 1-2 hours) when they do occur. If any of these side effects do occur, the subjects will be given a comfortable place to lie down until the symptoms pass, and will be monitored by the CTRC nurse and the project coordinator.

Studies of the pharmacokinetics of propranolol suggest that peak plasma concentrations following a 40 mg dose occur 1-2 hours after administration; as such, we will have participants rest quietly for 1 hour following administration of the medication before the start the stress task. Plasma half-life of propranolol is 3-6 hours, and as such, we will examine our more exploratory aims at the end of the session, which is still within the half-life of the drug.

The study MD will be on-call during all intervention sessions to assess any side effects and prescribe appropriate management as needed, and a CTRC nurse will be present throughout the majority of study procedures. Given that we do not anticipate any serious side effects to occur and that there is currently no data

to suggest that an acute dose of propranolol leads to serious side effects in healthy populations, we believe the facilities at Howell Hall are sufficient to manage the mild, transient side effects that may occur in response to taking propranolol.

1.4 Relevant Literature and Data

See Section 1.1 (Introduction) above and references at the conclusion of this proposal for a literature review and references.

2 STUDY OBJECTIVE

The purpose of this study is to determine if SNS activation is a key physiological mechanism linking psychological stress and inflammation. Thus, we will experimentally-block SNS activation using propranolol, a beta-blocker, and examine if exposure to propranolol attenuates inflammatory responses to a psychological stressor.

2.1 Primary Objective

Primary Objective 1. To examine if blocking sympathetic nervous system activity via the beta-blocker propranolol will attenuate inflammatory responses to stress.

2.2 Secondary Objectives

Secondary Objective 1. To examine if blocking beta-adrenergic receptors with the drug propranolol will attenuate cortisol responses to an acute, laboratory stressor.

Secondary Objective 2. To examine if blocking beta-adrenergic receptors with the drug propranolol will attenuate salivary alpha amylase responses to an acute, laboratory stressor.

Secondary Objective 3. To evaluate if blocking beta-adrenergic receptors with the drug propranolol will attenuate sympathetic nervous system responses (i.e., pre-ejection period; PEP) to an acute, laboratory stressor.

Secondary Objective 4. To examine if blocking beta-adrenergic receptors with the drug propranolol will change parasympathetic nervous system responses (i.e., respiratory sinus arrhythmia; RSA) to an acute, laboratory stressor.

Secondary Objective 5. To examine if blocking beta-adrenergic receptors with the drug propranolol changes self-reported psychological responses (i.e., negative affect) to an acute laboratory stressor.

3 INVESTIGATIONAL PLAN (brief overview)

3.1 Study Design

This is a double blind, randomized, placebo-controlled trial of the effects of propranolol on inflammatory responses to psychological stress in healthy participants. We will use a between-subjects manipulation, given that repeated exposures to the stress task may lead to habituation in both psychological and physiological responses, introducing a potential confound in order-effects. It consists of three stages: 1) telephone screening 2) in-person Session I and 3) in person Session II.

Telephone screening. The telephone screening will be conducted by trained research assistants in the Carolina Social Neuroscience and Health Laboratory, under the supervision of the PI. Inclusion and exclusion criteria will be assessed, and study procedures will be described. If participants meet inclusion criteria and are interested in participants, they will be scheduled for Session I.

Study Session I. Session I will last approximately 30-60 minutes. Participants will enter the lab in Howell Hall at UNC-Chapel Hill, meet the research assistant who is running the session, and read through the consent form. Once participants have been given a chance to ask any questions about the consent form and it is clear that they understand the protocol and are comfortable with proceeding, they will sign a copy of the General Consent Form. Next, subjects are informed in greater detail about the procedure for a heartbeat detection task as a measure of their interoceptive or inner bodily awareness. Task descriptions, instructions, and an opportunity to ask questions will be provided to each participant. The heartbeat detection task will take about 20 minutes to complete, and will be administered by trained research assistants. Following completion of the

heartbeat detection task, the experimenter will reiterate to the participant the general purpose of Session II and remind participants of their scheduled date for Session II.

Study Session II. Session II will last approximately 5 hours and will take place in the emotion induction laboratory in Howell Hall at UNC-CH. When the participant arrives for the session, they will meet the lab manager and the nurse supplied by CTRC. The lab manager will give the participant a chance to review the consent form signed during Session I, and will then remind the participant of the protocol and tasks in Session II. Once the participant understands the protocol and is comfortable with proceeding, the nurse will insert a catheter into the participant's non-dominant forearm, which will be used to draw all the blood samples. Over the course of the five hours, there will be five blood draws, four saliva samples, and a series of questionnaires. The participants will also complete the Trier Social Stress Task during. For this, the participant will give a short speech (10 minutes) while they are evaluated by trained research assistants. Participants will also complete a number of computerized tasks designed to assess our secondary aims. Participants will be fully debriefed at the end of the study.

3.2 Allocation to Treatment Groups and Blinding

The UNC Investigational Drug Service (IDS) will randomly assign patients to the experimental group (propranolol) or the placebo group. The randomizer will be instructed that groups should be matched on age, gender, and racial composition, and will thus be informed of the participant's demographic information in advance of randomization. Research staff who have direct contact with the participant will be blind to the condition of the participant. The psychiatrist who is monitoring safety and possible adverse events while the participants are on propranolol or placebo will be unblinded during the study and therefore able to identify which pill was taken if there are any significant adverse effects felt by the participant after taking the pill. The psychiatrist will not have direct contact with participants during the experimental visits unless the participant is experiencing adverse side-effects. Thus, no study team member who interacts with participants on the propranolol/placebo Session II visit will know whether a participant is on placebo or propranolol. After data collection for the study is completed, the pharmacist who made order assignments will reveal which group participants were in (propranolol vs. placebo) so appropriate analyses can be conducted.

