Saliva Samples. We will take 4 saliva samples during the study via the passive drool method. Passive drool is a saliva collection method for collecting whole saliva. Passive drool is considered by many researchers to be the gold standard when collecting saliva samples for biological testing, because it provides the purest sample possible and allows researchers to "biobank" samples for testing. Participants allow saliva to pool in mouth, then, with head tilted forward, gently force saliva through a small straw and into the vial. Participants will be aided by trained research assistants wearing rubber gloves. About 2ml of saliva will be collected at each sampling time. Saliva samples will be assayed for levels of the stress hormone, cortisol, as well as another HPA axis byproducts including ACTH and testosterone.

Blood Samples. We will draw 10 mL of blood into vacutainer EDTA tubes at each time point, which will be stored on ice for the duration of the study, and then centrifuged to isolate plasma and stored in 1 mL aliquots in cryovials in a -80 degree freezer until the study is complete. Samples will then be assayed for levels of pro-inflammatory cytokines (i.e., interleukin-6, tumor necrosis factor alpha, interleukin-1) using multiplex bead-based assays.

Psychophysiology. We will collect electrocardiogram and impedance cardiography data from participants to examine how propranolol and exposure to the TSST influence autonomic physiology.

Questionnaires (for exploratory moderator analyese):

Demographics.

We ask participants' age, gender, race/ethnicity, weight/height (to calculate BMI), perceived SES, and also about participants' comfort with giving speeches / being the center of attention.

Health Behavioral Questionnaire ([name], 2016). This asks a series of questions to make sure that participants followed instructions prior to the session and are still eligible to participate. It includes items "Which medications have you taken in the last 48 hours?"

UCLA Loneliness Scale: (Russell, D., Peplau, L.A., and Ferguson, M.L 1978) This is a commonly used, 10 item, measure of loneliness.

The PHQ-9: (Spitzer, 1999) This a multipurpose, validated instrument for screening, diagnosing, monitoring and measuring the severity of depression.

Perceived Stress Scale: (Cohen, 1994) This is a widely used psychological instrument for measuring the perception of stress; i.e the degree to which situations in one's life are appraised as stressful.

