6.1 Primary Endpoint- Statistical Methods

Primary Objective 1. To examine if blocking sympathetic nervous system activity via the beta-blocker propranolol will attenuate inflammatory responses to stress.

Analysis Plan. To address this aim, we will first examine if there was a change in inflammation simply as an effect of taking the propranolol (before stress induction). As such, we will conduct a multilevel model (MLM) examining levels of inflammation (IL-6), with time (BL vs. pre-TSST) as a within-subjects factor and condition (propranolol vs. placebo) as a between-subjects factor. If the result of this test shows a significant interaction, then we will only include the pre-TSST time point in subsequent models. If non-significant, we will use both baseline time points in subsequent analyses. Next, we will conduct an MLM examining levels of inflammation, with time (BL and/or pre-TSST, 30-, 60-, 90-min post-TSST) as a within-subjects factor and condition (propranolol vs. placebo) as a between-subjects factor. We hypothesize that individuals in the placebo condition will show an increase in levels of inflammatory markers from pre- to post-TSST, while those in the propranolol condition will show significantly lower levels of inflammation over time compared to the placebo condition (i.e., no stress-related increase in inflammatory markers).

All outcomes will first be examined using histogram and scatterplot for assumptions of normality and homoscedasticity. Any variables that need to be log-transformed (e.g., cortisol, sAA, IL-6) will be before analyses are run. Across all models, we will evaluate if we need to control for sex, BMI, and objective SES.

Prior to analyses, we will also examine each outcome for outliers existing +/- 3 SDs from the mean within each time point within each condition. Outliers are excluded only within the time point where they were problematic but retained elsewhere to reduce data loss.

All data will be analyzed in R using the lme4 package. As time points are nested within individuals, we take a multilevel modelling approach with the inclusion of a random intercept to model individual differences in each outcome.

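### The treatment code may be released before assays, cardiac scoring and data decisions are final, because the release point is tied to an undefined end of data collection and not to a locked data set

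*Combined protocol and SAP*

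**What the plan says.** **Release of the code.** Section 3.2: "After data collection for the study is completed, the pharmacist who made order assignments will reveal which group participants were in". The sentence adds that the purpose is to allow the analyses. Section 8 gives the same rule in the same terms.

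**Who is blind.** Section 3.2: "Research staff who have direct contact with the participant will be blind to the condition of the participant". Assay staff, scorers of the cardiac recordings and analysts are not mentioned. Section 6 gives the analysis to the investigator and trainees of the same laboratory.

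**Primary endpoint.** Section 5, Blood Samples, keeps plasma "in a -80 degree freezer until the study is complete. Samples will then be assayed for levels of pro-inflammatory cytokines".

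**Cardiac endpoints.** Section 5, Psychophysiology: "We will collect electrocardiogram and impedance cardiography data from participants". The plan does not say when, how or by whom PEP and RSA are scored.

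**Data decisions.** Section 6.1 bases transformation on inspection of plots and leaves covariates open: "Across all models, we will evaluate if we need to control for sex, BMI, and objective SES". It screens for "outliers existing +/- 3 SDs from the mean within each time point within each condition", and chooses the baseline time points by a test of the condition-by-time interaction.

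**The concern.** A trial described as double-blind should hide the arm until the endpoint values and the data set are final. Here the blind is written around the visits. It protects the people who run Session II, but not the later steps that turn stored plasma and raw recordings into endpoints, or that decide how those endpoints enter the model.

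Three features make this more than a formality. The investigators state the direction of effect they expect in Section 6.1. The same laboratory collects and analyses the data, and no independent or blinded statistician is named. Some of the open steps involve judgement: scoring a cardiac recording, deciding from a plot whether to transform, and deciding whether a covariate is needed when no criterion is given. If the arm is known, each choice can lean towards the hypothesis without anyone intending it.

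**Working it through.** The plan states no figure on this point, so the check is one of sequence: for each step between the last visit and the primary test, does the text place it before release of the code?

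| Step | Where | Timing stated | Needs group labels? | Required before release? |
|---|---|---|---|---|
| IL-6 assay | Section 5 | After study completion | No | No |
| Saliva assays | Section 5 | None | No | No |
| PEP and RSA scoring | Section 5 | None | No | No |
| Log transformation | Section 6.1 | Before analysis | No | No |
| Covariate choice | Section 6.1 | None | No | No |
| 3-SD outlier screen | Section 6.1 | Before analysis | Yes, within condition | No |
| Choice of baseline points | Section 6.1 | Before the main model | Yes, interaction test | No |

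**What the two end points could mean.**

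- *Narrow reading.* Data collection ends with the last Session II visit. Section 4.1 (Intervention/Treatment procedures) and the heartbeat task description in Section 5 support this, since both use the term for recording from participants in a session. The code could then be released before any IL-6 value exists. The volume involved would be 90 participants (Section 6.4) × 5 draws (Section 3.1) = 450 plasma samples.
- *Broad reading.* Data collection includes the assays. IL-6 would then come before release, but the text still does not place cardiac scoring, transformation or covariate choice before it.

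On either reading some steps are unprotected. Only the position of the assay changes.

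**The two rules that need groups.** The outlier screen and the baseline test cannot be run without knowing who belongs together. The plan does not provide masked labels, so as written both would use the true arms. A later release date alone would therefore not work: the data set could not be finalised without the labels being withheld.

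**Safeguards looked for elsewhere.** Section 10 replaces names with codes on data sheets. That hides identity, but it does not hide the arm from anyone holding the released list. Neither a database lock nor a blind data review is described.

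**Can the covariate choice be sized?** Write the planned random-intercept model as y(i,t) = a(i) + b·x(i) + condition + time + condition×time + e(i,t), where x(i) is sex, BMI or SES. In a person's post-minus-pre difference, a(i) and b·x(i) both cancel. With complete data, covariates entered as main effects therefore leave the condition-by-time test essentially unchanged. A simulated check (90 people, 5 times, all 2³ = 8 covariate sets, assumed within-person correlation) agrees. The p-value moved by less than 0.00001 across sets with complete data. With 5% of values missing at random, the median spread was about 0.004 to 0.013. The choice has more leverage only if covariates interact with time or if the condition main effect is the reported test, and the plan specifies neither.

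**The case against.** The strongest reply is that the release sentence is tied to analysis, and IL-6 cannot be analysed before it is assayed, so a sensible site would finish the assays first. That is a reasonable reading, and the documents do not exclude it. It shows that the order is unstated, not that it is wrong. It does not cover scoring or data decisions.

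A second reply is that little can go wrong in the assay. IL-6 comes from a multiplex bead instrument and records carry codes. This largely stands, and it is why the assay is the smaller part of the concern. Section 6.1 also names IL-6, cortisol and sAA as examples for logging, so the scale is not a wholly free choice.

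A third reply is that late release cannot fully blind cardiac scoring, because Section 4.1 (Intervention/Treatment procedures) expects propranolol to lower heart rate. This also stands. The protection there is partial.

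Two stronger readings are tempting and should not be drawn:

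- A reader might infer that all 450 plasma samples will be assayed after unblinding. That follows only on the narrow reading of terms the plan does not define.
- A reader might attach an inflated type I error, for instance by simulating the best of several covariate or scale choices on a change score. Such a model is not the planned one, and main-effect covariates barely move the planned interaction test. It would describe deliberate picking, and it would measure nothing about assay or scoring bias.

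**Conclusion.** The point holds as a gap in the release rule. The written plan permits endpoint handling and data decisions by people who know the arm, and this is true on either reading of when data collection ends. It does not show that unblinded handling will occur or that the result will be biased.

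No numerical size can be given. The documents contain nothing from which assay or scoring bias could be estimated, and no false-positive rate should be quoted. In order of exposure, cardiac scoring and the transformation and covariate decisions come first, and the multiplex assay on coded samples comes last. The conclusion assumes that no unreferenced laboratory procedure already imposes a lock or blinds scorers; if one does, the protocol need only cite it. This is a cheap improvement, not a fatal flaw.

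**What to change.** In Sections 3.2 and 8, replace the release point. IDS keeps the code until:

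1. all plasma and saliva assays are final, including any repeats;
2. PEP and RSA scoring is final;
3. transformations, covariates and exclusions are fixed in a dated record;
4. the data set is locked.

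State also that assay staff, cardiac scorers and those making the data decisions work without the code until then.

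For the 3-SD screen within condition and the baseline versus pre-TSST interaction test, IDS supplies masked A/B labels. Heart rate and blood pressure should not be summarised by these labels before lock, since the expected drug effect would show which label is which.

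The cost is slightly later unblinding and a small administrative task for IDS (issuing labels) and the data manager (lock and decision record). No change to visits, samples or sample size is needed. Scorers may still guess the arm from individual traces, so the report should describe that step as only partly protected.
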